The Respiratory Therapist (RT) will perform the CLT on all enrolled patients. The patients will first be switched to volume assist-control (V-AC) with a respiratory rate of 10 breaths/min (to allow patient assist), constant flow of 60 l/min, and tidal volume set to match the average tidal volume currently being delivered during supportive ventilation. The RT will document the average exhaled volume over 3-5 breaths after switching to V-AC. The test will be performed by deflating the ETT balloon cuff with a 10 cc syringe, and: a) auscultation with a stethoscope to identify audible air leak around the ETT, and b) measuring the difference between the average

exhaled volume prior to cuff deflation and the average exhaled volume over 3-5 breaths after cuff deflation.

We define a “failed CLT” as the RT being unable to identify air leak during auscultation.

Patients randomized to the intervention arm will have the results of the CLT (whether failed or passed CLT) communicated to the treating physician; the treating physician will decide whether to proceed with extubation or not based on the CLT results. It is at the discretion of the treating physician to provide corticosteroids (4-5 mg of intravenous dexamethasone every six hours for up to 24 hours, with the last dose given one hour preceding extubation) and/or delay extubation by 24 hours should the patient fail the CLT²³.

In the control arm of this trial; the treating physicians and healthcare workers will be blinded to the results of CLT; therefore, the RT will proceed with extubation without delay or administering systemic steroid, regardless to the CLT results.

Patients, physicians, RCs, study investigators, adjudicators, and data analysts will be blinded to the results of CLT in the control group.

OUTCOMES

Feasibility Outcomes

Although we will report all clinical outcomes relevant for the future COMIC RCT, the primary outcomes of the COMIC Pilot Trial will be the following feasibility outcomes:

- 1) Consent Rate: a successful consent rate will be defined as 70% of SDMs or patients approached to consent, choosing to participate in the trial. This will be calculated as the overall proportion of SDMs or patients consenting out of those approached (with 95% CI). As this is a Pilot Trial, the consent rate will be reviewed monthly and if applicable, barriers to informed

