consent will be discussed and factors associated with improved consent as produced by the CCCTG Research Coordinators will be employed²¹.

2) Recruitment Rate: a successful recruitment rate will be defined as achieving enrolment of 40 patients, conventionally expressed as four patients per month over the duration of the trial. While the pilot trial is ongoing, recruitment will be reviewed weekly and the screening records will be reviewed monthly with the cases of missed eligible patients reviewed. If applicable, barriers to enrolment will be addressed to maximize recruitment. The recruitment metric will be measured and interpreted at the end of the pilot trial by calculating the mean number of recruited patients per active screening month.

3) Protocol Adherence: Successful adherence will be defined as $\geq 80\%$ of patients assigned to the intervention arm being treated as previously described. The adherence will be calculated as the proportion of patients that were assigned to the control arm being extubated after CLT being performed and the portion of people that assigned to the intervention arm who are given the prescribed steroids for a failed CLT. As this pilot trial is ongoing, we will review adherence monthly and investigate the reasons for compliance failure. All reasons for either failure to extubate after a failed CLT in the control arm will be investigated. The RC will review the Respiratory Therapists' notes, and the medication profile to determine actual compliance. All reasons for non-compliance will be recorded for both groups using distinguishing clinical reasons (eg. Palliation, death, consent withdrawal, errors).

Clinical Outcomes

The clinical outcomes are:

- 1) Postextubation stridor: defined as an audible high pitched inspiratory noise caused by turbulent airflow through the narrowed airway that is detectable with or without a stethoscope within 48 hours of extubation.
- 2) Clinically significant postextubation stridor: Defined as stridor (see definition above) that requires medical intervention such as the administration of systemic steroids, racemic epinephrine, or Heli-ox.
- 3) Reintubation: defined as reintubation within 72 hours of original extubation while in the ICU. Reasons for intubation will be recorded.
- 4) Emergency surgical airway: defined as performing urgent tracheostomy or cricothyroidotomy for a life-threatening airway obstruction.
- 5) In ICU mortality.
- 6) In hospital mortality truncated at 30 days.

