- 7) Duration of mechanical ventilation: defined as time on the ventilator after randomization in days.
- 8) ICU length of stay in days.

Clinical outcome adjudication

The RC will enter data in a web-base and send relevant clinical information to staff at the methods centre who will validate data and prepare adjudication packages for all clinical outcomes. Two independent blinded physicians will adjudicate post extubation stridor and reintubation outcomes.

Data collection and follow-up

The RC will screen the ICU Monday to Friday to avoid incurring additional weekend on-call costs. RC will collect information including the patient baseline data (e.g., demographics, illness severity, advanced life support including duration of mechanical ventilation, daily data (e.g., CLT results, postextubation stridor, rate of reintubation, steroids administered), and source documentation that will help with adjudication of outcomes. RC will review patients daily in the ICU where the trial data including mortality, length of stay, and length of mechanical ventilation will be gathered. Once patients are discharged from the ICU they will no longer be followed daily, but incidence of in hospital mortality will be assessed at time of hospital discharge. Mortality, duration of ventilation, and ICU stay outcomes will be censored at 60 days.

Duration of the COMIC Pilot Trial

We anticipate that 10 months will be required to recruit 40 patients. A subsequent three months will be needed to validate the data, adjudicate the outcomes, analyze, interpret and present results. The total duration of the Pilot Trial may take up to 13 months to complete.

Analysis of the COMIC Pilot Trial

Calculation of consent and recruitment feasibility outcomes for the COMIC Pilot Trial will not require analysis by group, however compliance rates will have to be assessed for each group. Therefore, clinical outcomes will be analyzed as means or proportions in each arm. In addition, given the small sample size and short duration, we will not conduct any subgroup or interim analyses. An independent data safety and monitoring board will be created for the large COMIC RCT.

The proportion of patient in the two groups with the primary and secondary outcomes will be

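### The control-arm adherence calculation omits the no-delay, no-steroid and withheld-result conditions that define the control treatment, so a delayed or steroid-treated control patient who is later extubated counts as adherent

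*Protocol*

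**What the plan says.** The Intervention section of the protocol describes the control arm by three features. The result is withheld: "the treating physicians and healthcare workers will be blinded to the results of CLT". The other two concern timing and treatment: "the RT will proceed with extubation without delay or administering systemic steroid, regardless to the CLT results".

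Feasibility Outcomes, item 3 (Protocol Adherence), then gives the calculation for this arm: "The adherence will be calculated as the proportion of patients that were assigned to the control arm being extubated after CLT being performed". The success level of at least 80% is worded for the other arm, as the share "of patients assigned to the intervention arm being treated as previously described".

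The same item provides for checking. "The RC will review the Respiratory Therapists' notes, and the medication profile to determine actual compliance". It adds: "All reasons for either failure to extubate after a failed CLT in the control arm will be investigated". And: "All reasons for non-compliance will be recorded for both groups using distinguishing clinical reasons". Data collection and follow-up lists "daily data (e.g., CLT results, postextubation stridor, rate of reintubation, steroids administered" among what is gathered. The analysis section says that compliance is to be assessed separately for each group.

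**The concern.** The control treatment and the measure of adherence to it do not match. In the intervention arm, the physician may respond to a failed CLT with steroids, a 24-hour delay, or both. A patient managed that way will usually still be extubated after a CLT. The control-arm calculation asks only for that last event, so it cannot tell control management from intervention management in a patient who is eventually extubated.

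This matters because the control arm poses the harder feasibility question: will patients with a failed, undisclosed test be extubated promptly and without steroids? The Discussion says that physician acceptance is uncertain and that adherence must be examined before a large trial is pursued. A figure that stays high when the comparator has drifted towards the intervention would give false reassurance about separation between the arms.

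**Working it through.** **The conditions side by side**

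| Feature of control treatment (Intervention section) | In the adherence calculation? | Visible in planned data? |
|---|---|---|
| CLT performed | Yes | Yes |
| Extubated | Yes | Yes |
| No delay | No | Yes: respiratory therapist (RT) notes |
| No systemic steroid | No | Yes: medication profile, daily steroid data |
| Result withheld from treating team | No | No item named |

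The one control-arm failure singled out for investigation is failure to extubate after a failed CLT. Delay and steroid use are not named there.

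**Inputs**

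- Sample size: 4 patients per month × 10 months = 40, which reproduces the protocol's figure.
- Allocation 1:1, so 40 / 2 = 20 controls. The protocol does not state the number per arm; this is an assumption.
- Number of controls delayed or given steroids (c): not given in the protocol. The values below are illustrative.
- All 20 controls are assumed to be extubated eventually.

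**Formulas**

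- Rate as stated = extubated after CLT / all controls = 20/20.
- Rate on the Intervention section's no-delay and no-steroid conditions = (20 − c)/20.
- Intervals are exact (Clopper-Pearson) 95%.

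| c | As stated | On the Intervention section's conditions |
|---|---|---|
| 0 | 20/20 = 100% (83.2% to 100%) | 20/20 = 100% (83.2% to 100%) |
| 2 | 100% | 18/20 = 90% (68.3% to 98.8%) |
| 4 | 100% | 16/20 = 80% (56.3% to 94.3%) |
| 5 | 100% | 15/20 = 75% (50.9% to 91.3%) |
| 10 | 100% | 10/20 = 50% (27.2% to 72.8%) |
| 20 | 100% | 0/20 = 0% (0% to 16.8%) |

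**How many controls are likely to fail the CLT**

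The Introduction cites pooled sensitivity 0.56 and specificity 0.92 for laryngeal edema, and a prevalence of 4% to 55%. Applying these to this trial is an assumption: high-risk patients are excluded, and the trial defines failure by auscultation. With prevalence p, the failure rate is f = (1 − 0.92) + (0.56 + 0.92 − 1)p = 0.08 + 0.48p.

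- p = 0.04: f = 0.0992, so 20 × 0.0992 = 2.0 controls.
- p = 0.55: f = 0.344, so 20 × 0.344 = 6.9 controls.

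The patients in whom the arms should differ therefore number about 2 to 7. If every one of 2 is managed as described, the exact 95% CI is about 16% to 100%; if every one of 7 is, about 59% to 100%.

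**The case against.** The strongest reply is that the paragraph should be read whole. Eligibility requires an extubation order, and control patients are to be extubated promptly, so extubation after the CLT may simply mean the extubation that directly follows it. A patient held for a day because of a failed test could then be caught as a failure to extubate. The research coordinator's review of RT notes and medications is meant to establish actual compliance, reasons for non-compliance are recorded in both groups, and a full statistical analysis plan is promised, where coding rules are commonly set.

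Much of this stands. A reader might infer that the trial has no check on contamination and could not detect it. The documents do not support that: delay and steroid use are both visible in data already planned. What remains is narrower. The protocol states a formula for a primary outcome, and no sentence says that delay or steroid use takes a control patient out of its numerator. This is a stated rule that departs from the treatment definition, not detail left for later.

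A reader might also infer that the 80% level would be passed whatever happens to failed-CLT controls. That does not hold either. The level is worded for the intervention arm only. If it were applied to controls and none of the failed-CLT patients were extubated, the expected rate would be 1 − f. This is 80% at p = 0.25, but 65.6% at p = 0.55. It is also only an expectation: with 20 controls and f = 0.20, the chance of at most 4 failures is about 0.63.

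**Conclusion.** The point holds as a mismatch between two sections of the protocol. Followed literally, the control-arm calculation counts a patient as adherent who was delayed or given steroids and then extubated. With 20 controls all eventually extubated, 5 such patients leave the stated figure at 100% against 75% on the Intervention section's conditions.

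The size rests on an assumed 20 controls and an illustrative count, because the protocol gives no contamination rate. A fully contaminated arm would score 100% only if every control were eventually extubated; a control never extubated would lower the rate. That extreme also supposes that the planned blinding has broken down throughout, which nothing in the documents suggests. The correction is worth making because this is a primary outcome and most of the data needed are already planned.

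**What to change.** Reconcile the Protocol Adherence item with the Intervention section:

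- Define control-arm adherence as treatment according to the Intervention section: result withheld, no delay to extubation and no systemic steroid, regardless of the CLT result.
- Have the sponsor make the no-delay condition measurable, and say how steroids given for an unrelated reason are scored.
- State that the review of RT notes and medication profile decides who enters the numerator.
- Record with a yes/no item whether the result was disclosed to the treating team.
- Report n/N with an exact 95% CI for all control patients.
- Report the same figure descriptively for failed-CLT controls at final analysis, once results can be linked without breaking the stated blinding. Research coordinators and data analysts are both blinded to control-arm results, so the linkage must be planned.
- Do not make that subset the go/no-go criterion: with about 2 to 7 patients it cannot carry the decision.

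The cost is a change of outcome wording, the one added data item and the linkage step. The adherence figure may be lower, and the subset result will be very imprecise.

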**Cuff Leak Test and Airway Obstruction in Mechanically Ventilated ICU Patients
(COMIC): A Pilot Trial**

NCT: Not applicable

Date of Document: Dec 7, 2017

Cuff Leak Test and Airway Obstruction in Mechanically Ventilated ICU Patients (COMIC): A Pilot Randomized Controlled Trial Protocol

ABSTRACT

Introduction: Endotracheal intubation and mechanical ventilation are lifesaving interventions that are commonly done in the intensive care unit (ICU). The act of intubating someone can cause laryngeal edema that, if extensive enough, can cause airway obstruction after a patient is extubated. To date, the only test that is available to predict this complication is the cuff leak test (CLT). However, its diagnostic accuracy is uncertain as there have been no randomized controlled trials (RCT) examining this. Herein, we report the protocol for the Cuff leak and airway Obstruction in Mechanically ventilated ICU patients (COMIC) Pilot Trial to determine the feasibility of conduction a powered RCT to examine the impact of CLT on postextubation stridor and reintubation. Subsequently, describing the diagnostic accuracy of this test.

Methods: This will be a multi-center centered, pragmatic, double blinded RCT. We will include mechanically ventilated patients in the ICU, who are deemed ready to be extubated. All patients will have a CLT done prior to extubation. The results of the CLT in the intervention arm will be communicated to the treating physician, and decision to extubate will be left to the treating team, while the results of the CLT for patients in the control arm will not be communicated to the treating physician, and the patient will be extubated, regardless of the result of the CLT.

Objective: Although we will examine all clinical outcomes relevant for the future COMIC RCT, the primary outcomes of the COMIC Pilot Trial will be feasibility outcomes including: consent rate, recruitment rate, and protocol adherence. Clinical outcomes will include postextubation stridor, reintubation, emergency surgical airway, ICU mortality, in hospital mortality, duration of mechanical ventilation, and ICU length of stay in days.

INTRODUCTION

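### The stated calculation of protocol adherence counts discretionary steroids, has no denominator, and leaves out what separates the two arms

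*Protocol*

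**What the plan says.** The Abstract (Methods) separates the arms by who learns the CLT result. Results "in the intervention arm will be communicated to the treating physician, and decision to extubate will be left to the treating team", whereas "the results of the CLT for patients in the control arm will not be communicated to the treating physician".

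The Intervention section repeats this. "Patients randomized to the intervention arm will have the results of the CLT (whether failed or passed CLT) communicated to the treating physician", who then decides whether to go ahead with extubation. After a failed test, "It is at the discretion of the treating physician to provide corticosteroids", to delay extubation by 24 hours, or to do both. In the control arm the treating staff are blinded to the result and "the RT will proceed with extubation without delay or administering systemic steroid, regardless to the CLT results".

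Outcomes, Feasibility Outcomes, item 3 (Protocol Adherence) contains two statements:

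- The success criterion is at least 80% "of patients assigned to the intervention arm being treated as previously described".
- The calculation is "the proportion of patients that were assigned to the control arm being extubated after CLT being performed", together with "the portion of people that assigned to the intervention arm who are given the prescribed steroids for a failed CLT".

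The same item has the research coordinator review the respiratory therapists' notes and the medication profile, and record reasons for non-compliance in both groups. The analysis section requires compliance by group. The Discussion says the adherence rate must be examined before a large trial is pursued.

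**The concern.** The success sentence points back to the Intervention section. The calculation sentence that follows it measures something else.

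In the intervention arm it counts receipt of a drug that the protocol leaves to the physician. A physician who is told of a failed test and only delays extubation, or goes ahead with it, has followed the protocol but does not add to the count. Communication of the result, which is the one thing required for every patient in that arm, is not counted.

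In the control arm the count needs only a test followed by extubation. A patient whose result was disclosed, or who was given a steroid, or who was extubated late, still counts as adherent.

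The rate is meant to inform the main trial. It could look poor because clinicians used permitted discretion, or look good although the contrast between the arms had broken down.

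**Working it through.** **Inputs from the protocol.** Four patients per month (Recruitment Rate) over 10 months (Duration of the COMIC Pilot Trial) gives 4 × 10 = 40, which reproduces the stated enrolment. Allocation is 1:1, so about 40 / 2 = 20 per arm. The 80% criterion over 20 patients means 0.80 × 20 = 16.

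**Assumptions.** The protocol gives no CLT failure rate and no deviation rate. The counts below are illustrations: 3 failed and 17 passed tests among 20 intervention patients.

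**Requirement against calculation**

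| Element of the Intervention section | In the calculation? |
|---|---|
| Intervention: result communicated | No |
| Intervention: steroids after a failed test (optional) | Yes, as if due |
| Intervention: delay alone, or extubation, after a failed test (permitted) | Not credited |
| Control: result withheld | No |
| Control: extubated | Yes |
| Control: no delay, no systemic steroid | No |

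**Intervention arm, two cases**

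- Case A: all 20 results are communicated. Of the 3 failures, one is given steroids, one is delayed only and one is extubated. All 20 follow the protocol.
- Case B: all 3 failures are given steroids, but 5 of the 17 passed results are never communicated.

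| Reading | Case A | Case B |
|---|---|---|
| Success sentence (treated as described) | 20/20 = 100% | (20 − 5)/20 = 75% |
| Calculation, denominator failed tests | 1/3 = 33% | 3/3 = 100% |
| Calculation, passed patients counted as adherent | (17 + 1)/20 = 90% | (17 + 3)/20 = 100% |
| Calculation, denominator all intervention patients | 1/20 = 5% | 3/20 = 15% |
| Calculation, 'prescribed' read as ordered | 1/1 = 100% | 3/3 = 100% |

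In Case A the calculation understates adherence on three of its four readings. In Case B it overstates adherence on three of four.

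**How far the denominator matters.** Suppose n tests fail and exactly one of those patients is, permissibly, not given steroids.

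- Over failed tests the rate is (n − 1)/n: 0%, 50%, 67%, 75% and 80% for n = 1 to 5.
- If patients who passed count as adherent, it is 19/20 = 95% for every n.
- Over all 20 patients, at least 16 would have to fail and receive steroids before 80% could be reached.
- If no test fails, the rate over failed tests is undefined. The chance of that is (1 − f)^20: 0.95^20 = 0.36 at an assumed failure rate of 5%, 0.90^20 = 0.12 at 10%, and 0.80^20 = 0.01 at 20%.

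**Control arm.** Let all 20 be extubated after the test, with 5 having a disclosed result, a steroid or a delay. The calculation gives 20/20 = 100%. Management as the Intervention section requires is (20 − 5)/20 = 75%.

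**The case against.** The strongest reply is that the 80% criterion belongs to the success sentence, not to the calculation. That sentence refers back to the Intervention section, so it takes in communication, and it gives the right answer in both cases above (100% and 75%). This is correct. But the protocol then says how adherence will be calculated, and that calculation does not deliver what the success sentence asks for.

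Second, 'prescribed' may mean ordered by the physician, which fits the review of the medication profile. That reading removes the clash with discretion. It then measures whether ordered drugs were given, and communication and disclosure are still not counted.

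Third, a reader might infer that a single permitted decision against steroids makes the trial miss 80%. The documents do not support this. It holds only if failed tests are the denominator and there are four or fewer of them. If patients who passed count as adherent, the rate is 95%.

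Fourth, part of the control-arm gap is covered elsewhere. Failures to extubate after a failed control test are investigated, reasons for non-compliance are recorded, and steroids administered are collected. A steroid given to a control patient would therefore be seen, although it would not change the calculated rate. Nor does the control example cross a stated threshold, because the 80% names only the intervention arm.

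Finally, the Discussion frames the question as using the test against not using it, so whether clinicians act on the result does matter. That is a reason to describe steroid use and delay, not to score a permitted decision as non-adherence.

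**Conclusion.** The point stands and should be fixed. The adherence calculation conflicts with the Intervention section and with the success sentence beside it, and it states no denominator. This is not detail left to a statistical analysis plan: the protocol itself states the calculation of a primary outcome, and on terms that do not match its own intervention.

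The rate can err in either direction. In the Case A illustration, full compliance is reported as anything from 5% to 100% according to the reading. In the other direction, 75% compliance can be reported as 100% in either arm. These sizes rest on 20 patients per arm and on assumed numbers of failures and deviations; nothing in the protocol suggests that deviations of this size are likely. The mismatch itself needs no assumption.

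The consequence is limited. A reader might infer that the error would decide whether the main trial goes ahead, but the protocol attaches no stop/go rule to the 80%. Consent and recruitment rates are unaffected.

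**What to change.** Replace the calculation sentence in item 3 with two rates, each over all randomised patients in the arm:

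- **Intervention:** CLT done, result communicated to the treating physician before extubation, and management within the options that the Intervention section permits. Apply the existing 80% criterion here.
- **Control:** CLT done, result not disclosed to the treating team, and patient extubated without delay or systemic steroid. Report this rate alongside; no new threshold is needed.

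The time point should be extubation itself, not the decision to extubate, because the Population section already requires an extubation order for eligibility.

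Add one yes/no item on communication (intervention) or disclosure (control), recorded by the respiratory therapist who performs the test. Remove steroids from the intervention-arm calculation, and report steroid use and delayed extubation after a failed test descriptively.

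The cost is a wording change and one data item. The sources for steroid and extubation data are already in use. There are three drawbacks. Communication is an easy target, which is why the descriptive reporting is needed. Control-arm adherence may look less favourable. The team will also need a working time limit for delay in the control arm, since the protocol gives none.

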The COMIC (Cuff leak and airway Obstruction in Mechanically ventilated ICU patients) pilot trial will be a multicenter, randomized, concealed, blinded, parallel-group, pragmatic pilot trial.

Population

Eligible patients will be mechanically ventilated adults (>18 years) who are admitted to the ICU and an order to extubate has been provided by the treating physician.

Exclusion criteria

The exclusion criteria are:

- 1) A palliative care, a one-way extubation, or a decision to withdraw advances life support order has been written.
- 2) Pregnancy.
- 3) Patients at high risk for LE: burn patients, smoke inhalation injuries (as defined as singed facial hair or nasal hair, carbonaceous secretions/sputum, and known to be in an enclosed fire), blunt or penetrating trauma involving the neck and airway, postoperative head and neck surgeries, and patients admitted with airway edema to the ICU (e.g; anaphylaxis)¹⁸⁻²⁰.
- 4) Patients with either a difficult or traumatic endotracheal intubation.
- 5) Patients receiving mechanical ventilation via tracheostomy.
- 6) Known preexisting tracheolaryngeal abnormalities such as: vocal cord paralysis, tracheolaryngeal neoplasm, tracehomalasia, tracheolaryngeal stenosis, or previous head and neck surgeries.
- 7) Patients receiving systemic corticosteroids of greater than 30 mg of PO prednisone or equivalent, within 4 days prior to the decision to extubate.
- 8) Patients who failed extubation attempt within the current ICU admission.
- 9) History of postextubation airway obstruction.
- 10) The ICU physician declined enrolling the patient.
- 11) Patient had a failed CLT in the previous 24 hours.

Eligible non-randomized patients

We will record all patients who were eligible but not randomized for any of the following reasons: 1) The patient or substitute decision maker (SDM) declined consent; 2) The ICU physician declined enrolling the patient; 3) Any other reason.

Ethics

We will apply and obtain research ethics board (REB) approval at the participating centres. As most patients will be incapable at the time of enrolment, the SDM will provide consent *a priori* whenever possible. If the patient is able to consent at the time of enrolment then we will get written consent from them. We will follow the 2-phase, 13-step informed consent process that we have used in prior international trials²¹.

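### Reintubation is counted only in the ICU, so a ward reintubation within 72 hours scores as a non-event

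*Protocol*

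**What the plan says.** **Reintubation.** Protocol, Clinical Outcomes, item 3, gives the definition as "defined as reintubation within 72 hours of original extubation while in the ICU". It combines a time limit with a place.

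**Stridor.** Item 1 of the same list counts stridor that is "detectable with or without a stethoscope within 48 hours of extubation", with no place limit. Item 2, clinically significant stridor, takes over that definition: "Defined as stridor (see definition above) that requires medical intervention".

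**Follow-up.** Under Data collection and follow-up, "RC will review patients daily in the ICU". After ICU discharge, "they will no longer be followed daily, but incidence of in hospital mortality will be assessed at time of hospital discharge". Mortality is the only item named for assessment after the ICU stay. No minimum ICU stay after extubation is stated.

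**Adjudication and analysis.** Methods-centre staff "prepare adjudication packages for all clinical outcomes", and two blinded physicians adjudicate stridor and reintubation. Under Analysis of the COMIC Pilot Trial, "clinical outcomes will be analyzed as means or proportions in each arm".

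**The concern.** A 72-hour reintubation risk is normally understood as the share of extubated patients who are reintubated within 72 hours, wherever they are. With the ICU condition, how long a patient can be counted depends on when that patient leaves the ICU. Someone who stays 72 hours is observed for the whole window. Someone who leaves at 24 hours is observed for a third of it, yet enters the denominator in full and is scored as event-free. A simple proportion per arm does not allow for this.

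The Introduction names stridor and reintubation as the outcomes of the intended larger trial, and the Discussion says the pilot should inform that trial's design and conduct. An undercounted reintubation rate, or the restricted definition itself, could be carried forward. Adjudication cannot restore an event that the definition excludes.

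**Working it through.** **1. The plan's own figure.** Four patients a month for 10 months gives 4 × 10 = 40, as stated. Nothing in that target depends on the reintubation definition, so it does not change.

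**2. Can the wording be read another way?** The place phrase could be attached to the extubation instead of the reintubation. But the Population section enrols only adults "who are admitted to the ICU and an order to extubate has been provided by the treating physician", so on that reading the phrase adds nothing. Either it excludes ward reintubations or it is redundant. In both cases it can be deleted without losing anything that a 72-hour outcome needs.

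**3. Missed share of reintubations.** The protocol gives no ICU stay after extubation, no share of early leavers and no event timing, so every input below is an assumption. Let f be the share of patients leaving the ICU early and h the hours from extubation to ICU discharge. Early leavers are given the same risk as the others.

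- Even timing over 72 hours: missed share = f × (1 − h/72).
- Front-loaded timing (75% of events in the first 24 hours, the rest even over the next 48): missed share = f × 0.25 × (72 − h)/48, for h of 24 or more.

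| f (patients of 40) | h | Even timing | Front-loaded |
|---|---|---|---|
| 0.10 (4) | 48 | 0.10 × 24/72 = 3.3% | 0.10 × 0.25 × 24/48 = 1.3% |
| 0.25 (10) | 36 | 0.25 × 36/72 = 12.5% | 0.25 × 0.25 × 36/48 = 4.7% |
| 0.50 (20) | 24 | 0.50 × 48/72 = 33.3% | 0.50 × 0.25 × 48/48 = 12.5% |

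Lower risk in early leavers would shrink every entry.

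**4. In events.** Assume a true 72-hour reintubation risk of 5% to 15%, that is 2 to 6 events in 40 patients. The middle row then misses 2 × 0.125 = 0.25 to 6 × 0.125 = 0.75 events with even timing, or 0.09 to 0.28 front-loaded. The bottom row misses 0.7 to 2.0 events, or 0.25 to 0.75 front-loaded.

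**5. Stridor, if ward events were not captured.** Even timing over 48 hours gives f × (1 − h/48): 0%, 6.3% and 25.0% for the three rows. Front-loaded timing gives f × 0.25 × (48 − h)/24: 0%, 3.1% and 12.5%. These figures apply only under that condition, which the protocol does not state.

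**The case against.** **It is a coherent choice.** Reintubation is limited to the ICU and the daily data are gathered in the ICU, so definition and follow-up agree. That is true, and there is no contradiction on this outcome. But no reason is given for the limit, stridor carries no such limit, and the cost is a window that varies between patients.

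**The undercount is assumed and small beside sampling error.** This largely stands. An observed 4 of 40 has an exact 95% confidence interval of 2.8% to 23.7%, which is wide compared with a loss of less than one event in the middle case. The 33.3% corner needs half the patients to leave at 24 hours, equal risk and even timing. Nor does the protocol say that the pilot's event rates will set the larger trial's sample size. The rates it says must be examined first are recruitment, consent and adherence.

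**Stronger readings to resist.**

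- A reader might infer that ward stridor is lost. The protocol ends only the daily review. It also provides for source documentation and for adjudication packages covering every clinical outcome, so chart retrieval to 48 hours fits the text. What is missing is a description.
- A reader might infer a biased comparison between arms, because extubation may be delayed in the intervention arm after a failed test. No data on discharge timing by arm are given. With equal true risks and assumed missed shares of 30% in control and 10% in intervention, the apparent risk ratio is 0.90/0.70 = 1.29. With the shares swapped it is 0.70/0.90 = 0.78. The direction comes wholly from the assumption.

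**Conclusion.** The point holds for reintubation, at modest severity. As worded, the definition drops ward reintubations inside its own 72-hour window and gives patients unequal observation time for an outcome that the larger trial is to study. The illustrative missed share is about 1% to 33%, with 4.7% to 12.5% in the middle case. These figures rest on assumed discharge times, event timing and equal risk, and none of them comes from the documents. No direction between arms can be claimed. Consent rate, recruitment rate, protocol adherence and the target of 40 patients are untouched. For stridor, the undescribed ward capture calls only for a clarification.

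**What to change.** Delete the ICU condition from the reintubation definition and count reintubation to 72 hours after first extubation in any hospital location. For patients who leave the ICU before 72 hours, have the research coordinator check the chart once, at the hospital-discharge mortality assessment that already exists, and add the result to the adjudication package. Say in the same sentence that the check also covers stridor, including clinically significant stridor, to 48 hours.

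The cost is a wording change and one chart check per early ICU leaver among 40 patients (4 to 20 checks under the assumptions above), with no new contact point. The downside is that ward records of stridor are likely to be less complete than ICU records.

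If the sponsor prefers to keep the ICU limit, the fallback is to state it explicitly for both outcomes and report how many patients in each arm left the ICU before each window closed. That makes the shortened observation visible but does not recover the events.
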